## 9 STATISTICAL METHODS

### 9.1 Sample size calculations

For the parallel cluster study in Phase 1, the primary analysis will evaluate whether the use of ePOCT+ for case management of sick children in PHC facilities results in decreased antibiotic prescriptions (superiority analysis) at the initial consultation. Superiority in antibiotic prescription is defined as a relative decrease of  $\geq 25\%$  in the proportion of children prescribed an antibiotic. We estimated a cluster size of 660 patients (monthly utilization of 220 – accounting for up to 30% non-adherence from 315 – over 3 months) and an intraclass correlation coefficient of 0.025. Non-adherence here is defined as HWs not using the application for all eligible patients that come to the HF for various reasons. To have 80% power to detect a 25% reduction in antibiotic prescription (e.g. from 35% to 26%), for a one-sided hypothesis test at alpha of 0.05, we would require a minimum of 11 clusters per arm. With 16 clusters (or HF) over 3 months, we expect a total of 10,500 participants per arm, this sample size is

sufficient to test for non-inferiority in the secondary outcome (clinical cure at day 7) between the control and intervention groups.

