Statistical considerations	
For the parallel cluster study in Phase 1, the primary analysis will evaluate whether the use of ePOCT+ for case management of sick children in PHC facilities results in decreased antibiotic prescriptions (superiority analysis) at the initial consultation. Superiority in antibiotic prescription is defined as a relative decrease of <math>\geq 25\%</math> in the proportion of children prescribed an antibiotic. We estimated a cluster size of 660 patients (monthly utilization of 220 – accounting for up to 30% non-adherence from 315 – over 3 months) and an intraclass correlation coefficient of 0.025. To have 80% power to detect a 25% reduction in antibiotic prescription (e.g. from 35% to 26%), for a one-sided hypothesis test at alpha of 0.025, we would require a minimum of 11 clusters per arm. With 16 clusters (or HFs) per arm, over 3 months, we expect a total of 10,500 participants per arm, this sample size is sufficient to test for non-inferiority in the secondary outcome (clinical cure at day 7) between the control and intervention groups.
 
We will test for significant difference in the primary outcome of antibiotic prescription between study arms by comparing proportions and their 95% confidence intervals. Primary analysis of superiority will be performed according to the intention-to-treat principle. The results will be stratified by sex, age group (young infants ages 1 to 59 days, children aged 2 months to 5 years, and children aged 5 to 14 years), and select clinical variables (respiratory symptoms, fever without clinical source, gastrointestinal complaints, skin problems, ear and throat problems, anemia, and malnutrition).
 
At the estimated utilization of the PHC facilities in Nyamasheke and Rusizi districts, we anticipate that approximately 150,000 consultations will be conducted using ePOCT+ throughout the study.

Study duration and schedule	
Pilot phase: April 2021 – August 2021
 
Phase 1 (data collection): September 2021 – April 2022
 
Phase 2 (data collection): June 2022 – December 2022
 
Implementation research (data collection): October 2020 – October 2022
 
Sustainability assessment: August 2022 – December 2022

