3.3 Sample size

The primary analysis will evaluate whether the use of ePOCT+ for case management of sick children in PHC facilities results in decreased antibiotic prescriptions (superiority analysis) at the initial consultation. Superiority in antibiotic prescription is defined as a relative decrease of $\geq 25\%$ in the proportion of children prescribed an antibiotic. We estimated a cluster size of 660 patients (monthly utilization of 220 – accounting for up to 30% non-adherence and/or loss to follow-up from 315 – over 3 months) and an intraclass correlation coefficient of 0.025. Non-adherence here is defined as HWs not using the application for all eligible patients that come to the HF for various reasons. To have 80% power to detect a 25% reduction in antibiotic prescription (from 35% to 26%), for a two-sided hypothesis test at alpha of

0.05, we would require a minimum of 11 clusters per arm. With 16 clusters per arm, over 3 months, we expect a total of 10,500 children in each study arm. Considering the pragmatic/adaptive nature of the study design, if a higher antibiotic prescription in the control arm is encountered (e.g. 45% or higher), each cluster study of 5-6 health facilities per study arm will be sufficiently powered to show a statistically significant reduction in the primary outcome. Sample size calculations were performed in R statistical software (version 4.0.3) using the CRTSize package (Rotondi, 2015).

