6.1 Analysis methods

Analyses will follow CONSORT guidelines (Campbell, Piaggio, Elbourne, & Altman, 2012; Piaggio et al., 2012; Schulz, Altman, & Moher, 2010; Zwarenstein et al., 2008). Outcomes will be described by arm using summary statistics. Baseline characteristics will be compared by study arm and by cluster study to ensure that the pragmatic allocation of health facilities and sequential rollout of the study did not introduce significant bias. Baseline characteristics which will differ between treatment arms within and over all clusters will be described using summary statistics.

Since the documentation of final treatment in both arms is part of the per protocol definition, only the PP population can be used for primary outcome analysis. The primary outcome will be evaluated using a random effects logistic regression model with the binary outcome variable of antibiotic prescription, with study arm and covariates at patient-level (e.g. age, sex) as fixed effects, and cluster (health facility) and patient included as random effects. Binary secondary outcomes will be evaluated in the same way. All estimates will be reported as odds ratios (ORs) with two-sided 95% confidence intervals (CI). The study will be deemed a success if antibiotic prescription at the initial consultation is 25% less in the ePOCT+ arm compared to the control arm, although we expect a greater reduction based on limited pilot data.

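### Protocol 9.1 sets the primary test at one-sided alpha 0.05, against the synopsis and SAP, and the quoted 11 clusters per arm does not follow from that level

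*Protocol*

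**What the plan says.** The sample-size paragraph appears three times: in the protocol synopsis (Statistical considerations), in protocol 9.1 and in SAP 3.3. All three use 80% power, a control rate of 35% falling to 26%, a cluster size of 660, an intraclass correlation of 0.025 and a minimum of 11 clusters per arm. They differ in the test level:

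- Protocol 9.1: "for a one-sided hypothesis test at alpha of 0.05, we would require a minimum of 11 clusters per arm".
- Protocol synopsis: "for a one-sided hypothesis test at alpha of 0.025, we would require a minimum of 11 clusters per arm".
- SAP 3.3: "for a two-sided hypothesis test at alpha of" "0.05, we would require a minimum of 11 clusters per arm".

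For the analysis, SAP 6.1 states: "All estimates will be reported as odds ratios (ORs) with two-sided 95% confidence intervals (CI"). Protocol 9.2 also plans 95% intervals and leaves further detail to the SAP.

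The effect is described as a 25% reduction. The SAP wording is "80% power to detect a 25% reduction in antibiotic prescription (from 35% to 26%), for a two-sided hypothesis test"; the protocol gives the same two rates as an example. All three paragraphs define superiority as a relative decrease of at least 25%. The trial plans 16 clusters per arm. No paragraph gives the power of 16 per arm for the primary outcome.

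**The concern.** A minimum number of clusters depends on the test level, so one number cannot be right for both one-sided 0.05 and two-sided 0.05 when every other input is the same. At least one stated level must be wrong, and the protocol alone does not tell the reader which governs the primary test, since its synopsis and section 9.1 disagree.

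The direction matters. One-sided 0.05 allows a 5% chance of falsely declaring a benefit. Two-sided 0.05 and one-sided 0.025 each allow 2.5%. The laxer level stands in the protocol's main statistical section.

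There is also a smaller mismatch. The rates used in the calculation are not exactly the reduction named beside them, and the stated minimum of 11 is close enough to its threshold for this to change the count.

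**Working it through.** **Inputs.** From protocol 9.1, repeated in the synopsis and SAP 3.3: p1 = 0.35, p2 = 0.26, m = 660 per cluster, ICC = 0.025, power 80% (z = 0.842). The 30% allowance is already inside m: 315 × 0.7 = 220.5, taken as 220 per month, and 220 × 3 = 660. Equal cluster sizes are assumed, because the documents give no measure of their spread.

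**Formulae.**
- Design effect: DE = 1 + (m − 1) × ICC = 1 + 659 × 0.025 = 17.475.
- Clusters per arm: k = (z_alpha + z_power)² × [p1(1 − p1) + p2(1 − p2)] / (p1 − p2)² × DE / m.
- Power at k clusters: Φ(|p1 − p2| / SE − z_alpha), with SE² = [p1(1 − p1) + p2(1 − p2)] × DE / (k × m).

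**Step 1: reproduce the plan's figure.** Take z_alpha = 1.960, which is both two-sided 0.05 and one-sided 0.025.
- Variance sum: 0.2275 + 0.1924 = 0.4199. Difference: 0.09.
- Individuals per arm before clustering: 7.849 × 0.4199 / 0.0081 = 406.9.
- k = 406.9 × 17.475 / 660 = 10.77, so 11. With a pooled variance, 410 × 17.475 / 660 = 10.86, also 11.
- Power at 11: SE = 0.0318, and Φ(2.831 − 1.960) = 80.8%.

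So 11 is correct for the synopsis and for the SAP.

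**Step 2: the level in protocol 9.1.** Take z_alpha = 1.645.
- Individuals per arm: 6.183 × 0.4199 / 0.0081 = 320.5.
- k = 320.5 × 17.475 / 660 = 8.49, so 9.
- Variants: pooled variance 8.55, continuity correction 9.13, t-based 9.32, one cluster added 9.49. None exceeds 10 after rounding up.
- Power at 11 at this level would be 88.2%, not 80%.

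**Step 3: the size of the reduction.**
- (35 − 26) / 35 = 25.7%. Exactly 25% is 0.35 × 0.75 = 26.25%.
- At z_alpha = 1.960: variance sum 0.2275 + 0.1936 = 0.4211, difference 0.0875, and 7.849 × 0.4211 / 0.007656 = 431.7.
- k = 431.7 × 17.475 / 660 = 11.43 (pooled 11.52), so 12.
- Power is 78.5% at 11 and 81.9% at 12.

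**Step 4: the planned 16 per arm, two-sided 0.05, equal cluster sizes.** The t figures use a noncentral t with 2(k − 1) = 30 degrees of freedom.

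| Alternative | Power, normal | Power, t |
|---|---|---|
| 35% to 26% | 92.7% | 91.0% |
| 35% to 26.25% | 91.2% | 89.4% |

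SAP 3.3 names the CRTSize package in R. That routine was not run here; the standard design-effect formula reproduces its 11.

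**The case against.** The best defence is that this is a slip in one sentence. The synopsis and the SAP agree numerically, the SAP plans two-sided 95% intervals, and protocol 9.2 defers detail to the SAP. The doubled error rate would arise only if the sample-size sentence in 9.1 governed the test. That is fair and limits the consequence. It does not remove the contradiction, since 9.1 is current text and its own inputs do not give 11.

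A reader might draw four stronger conclusions, and the documents do not support them.

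- *There are three different alphas.* One-sided 0.025 and two-sided 0.05 have the same critical value, so there are two levels.
- *Eleven clusters fail to give 80% power.* For the rates the documents use they give 80.8%. At the level in 9.1 they give more, 88.2% for 26% and 86.5% for 26.25%. The shortfall exists only for exactly 26.25% at two-sided 0.05. It is 1.5 points, comes from rounding 26.25% to 26%, and concerns a minimum that the trial exceeds.
- *The minimum should be 13.* That follows from t critical values with 26.25% (12.47). Such a correction is reasonable with few clusters, but the documents do not say one was used, so its absence is not an arithmetic error.
- *Unequal cluster sizes leave 16 per arm underpowered.* With DE = 1 + [(1 + CV²)m − 1] × ICC and an assumed coefficient of variation of cluster size of 0.4, 0.6 or 0.8, t-based power at 16 for 26.25% is about 85%, 79% or 72%. The documents give no such coefficient. The floor of 19 children under five per week is an eligibility threshold and does not measure spread, and SAP 5.2.1 excludes health posts, which may narrow it. These figures justify a check but do not show an error in the plan.

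**Conclusion.** The concern holds for the test level. Protocol 9.1 conflicts with the synopsis, SAP 3.3 and the intervals planned in SAP 6.1. Its one-sided 0.05 needs about 9 clusters per arm, not 11, and would double the false-positive rate for benefit from 2.5% to 5% if it were applied.

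A minor labelling point also holds: the calculation is for a 25.7% reduction, and exactly 25% at two-sided 0.05 needs 12 clusters.

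Neither point shows an underpowered trial. On the documents' own cluster size and intraclass correlation, and with equal cluster sizes, the planned 16 per arm have about 91% power (normal) or 89% (t) for exactly 25%. The planned size does not change on this ground.

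**What to change.** 1. State two-sided alpha 0.05 in the synopsis and in protocol 9.1, and keep it in SAP 3.3. It agrees with the planned intervals and with the quoted 11.
2. Match the alternative to its count in all three places: either 35% to 26%, labelled as a 25.7% reduction, with 11 clusters per arm; or 35% to 26.25%, exactly 25%, with 12.
3. State the power of the planned 16 per arm for the alternative chosen, with the method and the equal-size assumption. For 26.25% this is about 91% (normal) or 89% (t).
4. Optionally, add a sensitivity check for unequal cluster sizes, using the facility-level HMIS utilisation data that protocol 5.2 says were obtained.

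The cost is corrected wording and a few restated figures, made through the amendment route in protocol 11.5. Items 1 to 3 need no extra facilities, patients or data.

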## 9.2 Statistical analysis for the primary outcome measure in the parallel cluster study

Analyses will follow CONSORT guidelines (Schulz et al. 2010, Piaggio et al. 2012). A flowchart will describe the inclusion and follow-up of participants by study arm and by implementation block. Baseline characteristics and outcomes will be described by study arm and by implementation block using summary statistics such as median and interquartile range or number and percentage.

We will test for significant difference in the primary outcome of antibiotic prescription between study arms by comparing proportions and their 95% confidence intervals (CI). Primary analysis of superiority will be performed according to the intention-to-treat (ITT) principle (Committee for Proprietary Medicinal Products, 2001), with sensitivity analyses exploring differences between ITT, per-protocol and complete cases analysis approaches. The results will be stratified by sex, age group (young infants ages 1 to 59 days, children aged 2 months to 5 years, and children aged 5 to 14 years), and select clinical variables (respiratory symptoms, fever without clinical source, gastrointestinal complaints, skin problems, ear and throat problems, anemia, and malnutrition).

We will also use multi-level logistic regression with HF, patient ID, and time included as random effects (Kahan et al. 2012) to explore the effect of demographic and clinical variables on the outcome of interest. Effect modification by sex, age group, and the same clinical variables will be assessed by incorporating an interaction between arm and the respective variable, acknowledging that power will be low.

Primary analysis will be performed on initial consultations only (i.e. first visit for a particular illness episode), allowing multiple observations per patient over the course of Phase 1, but only one observation per illness. We will apply a 14-day period from the initial visit, during which no second initial visit will be possible and all subsequent visits will be marked as re-attendance by default. In the secondary sub-analyses, re-attendance visits between day 0 and day 7 will be considered, as well as longitudinal analyses of the complete visit history per patient. Further details on the primary and secondary analyses will be provided in the statistical analysis plan.

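### The protocol's stated primary test (arm proportions and 95% CIs, no allowance for clustering) conflicts with the facility random-effects model in SAP 6.1; with unadjusted CIs, false positives would be about 51–64%

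*Protocol*

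**What the plan says.** - **Protocol 9.2** tests for a significant difference in antibiotic prescription "between study arms by comparing proportions and their 95% confidence intervals (CI". The synopsis, under statistical considerations, has the same rule: "between study arms by comparing proportions and their 95% confidence intervals". Neither place says how the intervals allow for facilities.
- **Protocol 9.2, multilevel model.** "We will also use multi-level logistic regression with HF, patient ID, and time included as random effects". Its stated purpose is "to explore the effect of demographic and clinical variables on the outcome of interest", together with effect modification. The synopsis does not mention a model.
- **Protocol 9.2, population.** "Primary analysis of superiority will be performed according to the intention-to-treat (ITT) principle".
- **Protocol 9.2, closing sentence.** "Further details on the primary and secondary analyses will be provided in the statistical analysis plan".
- **SAP 6.1.** "The primary outcome will be evaluated using a random effects logistic regression model". Facility and patient are random effects, and results are odds ratios with two-sided 95% CIs. The population for the primary outcome is per-protocol only.
- **Protocol 9.1** sizes the trial for clusters of 660 with "an intraclass correlation coefficient of 0.025". It defines superiority as a relative decrease of at least 25%, as do the synopsis and SAP 3.3.

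**The concern.** The sample size allows for children in the same facility being alike, but the test written in the protocol does not. A comparison of two pooled proportions with ordinary binomial intervals treats about 10,500 children per arm as independent, when the information comes from 16 facilities. Such intervals are far too narrow, and chance differences between facilities would be read as an effect.

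The SAP has a suitable model, but it stands beside the protocol's rule without replacing it. On the same data the two can disagree on whether the primary outcome differs between arms, and no passage says which one decides.

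**Working it through.** **Inputs.** Cluster size m = 660, ICC = 0.025, 35% versus 26%, 80% power, minimum 11 clusters per arm (Protocol 9.1); 16 clusters per arm (Protocol 9.1, SAP 3.3); 5–6 facilities per arm in each block (SAP 3.3).

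**1. Reproduce the plan's figure.**
- Under independence, two-sided 0.05: n = [1.96·√(2 × 0.305 × 0.695) + 0.8416·√(0.2275 + 0.1924)]² / 0.09² = 410 per arm.
- Design effect = 1 + (660 − 1) × 0.025 = 17.475.
- Clusters per arm = 410 × 17.475 / 660 = 10.86, so 11.

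The plan's 11 is reproduced, and only with the design effect. It also follows from the one-sided 0.025 in the synopsis. The one-sided 0.05 printed in Protocol 9.1 gives 9, which is a separate inconsistency.

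**2. Size of the understatement.** The true standard error is √17.475 = 4.18 times one that ignores clustering. With 16 × 660 = 10,560 children per arm and 35% in both arms:
- SE of the difference ignoring clustering = √(2 × 0.35 × 0.65 / 10,560) = 0.0066, so a difference beyond 1.3 percentage points is declared significant.
- True SE = 0.0066 × 4.18 = 0.027, so chance alone gives differences of up to about ±5.4 points in 95% of trials.

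**3. False-positive rate with no effect, intervals not adjusted for clustering.**
- Ordinary test or CI of the difference: 2[1 − Φ(1.96 / 4.18)] = 63.9%.
- Non-overlap of two 95% CIs: 2[1 − Φ(1.96 × √2 / 4.18)] = 50.7%.

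A beta-binomial simulation (40,000 trials per setting) agrees:

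| Facilities per arm | Ordinary test | Non-overlap | t test on facility proportions |
|---|---|---|---|
| 16 | 63.9% | 50.8% | 5.1% |
| 6 | 64.0% | 51.1% | 5.0% |
| 5 | 64.2% | 51.0% | 5.2% |

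The inflation hardly depends on the number of facilities. It therefore applies equally to the within-block comparisons of Protocol 4.1.

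**4. Direction.** These rates count both directions. Half favour ePOCT+: 50.7% / 2 = 25% to 63.9% / 2 = 32%.

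**5. Sensitivity to the ICC (m = 660).** ICC 0.01 (design effect 7.59) gives 31–48%. ICC 0.05 (design effect 33.95) gives 63–74%.

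**6. Adding the 25% criterion.** Suppose success also needs an observed intervention rate at or below 0.75 times the control rate. The simulated false-success rate is 0.02% with 16 facilities per arm, 1.2% with 6 and 2.1% with 5. Hand check at 16: the SE of one arm is √(0.2275 / 10,560) × 4.18 = 0.0194. The SD of (intervention − 0.75 × control) is 0.0194 × √(1 + 0.75²) = 0.0243 and its mean is 0.25 × 0.35 = 0.0875, so z = 3.6 and the tail is about 0.02%.

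**7. With clustering allowed for.** Type I error is about 5% (last column of the table). Power for 35% versus 26% is 80.6% with 11 clusters per arm and 92.6% with 16 (two-sided 0.05, normal approximation).

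**The case against.** The strongest reply is that 9.2 leaves further details to the SAP, and the SAP names a model with a facility effect. The analysis most likely to be run is therefore sound. That stands as far as it goes. A reader might infer that the trial's primary analysis ignores clustering, and SAP 6.1 does not support that. But a different primary test is a replacement rather than a detail, and nothing says expressly that it replaces the one in 9.2. The two sections also disagree on the primary population, so the SAP cannot be read as only filling in 9.2.

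Second, the 51–64% depends on unadjusted intervals. No passage says they will be unadjusted, so the figure must carry that condition.

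Third, a reader might infer that the protocol rule fails however it is read, because judging two separate cluster-adjusted 95% CIs by overlap is a test at about 0.6%: 2[1 − Φ(1.96 × √2)]. The documents do not support that either. They state no overlap rule, and comparing the proportions through a cluster-adjusted CI for their difference is a valid test at about 5%.

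Fourth, the 25% requirement makes a false declaration of success rare, especially with all 16 facilities per arm. This is right if the 25% applies to the observed result, as the success statement in SAP 6.1 suggests. It does not protect the significance test that 9.2 describes separately.

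Last, one might say that an ethics committee has approved the faulty test. Protocol 11.5 describes approval only as something to be obtained.

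**Conclusion.** The concern holds in a conditional form. The protocol and the SAP give two different primary tests. The protocol's version, on its plain reading, is invalid for a trial with 660 children per facility and an ICC of 0.025: about 64% false positives for an ordinary test of the difference and 51% for non-overlap.

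These figures rest on intervals computed without allowance for clustering, equal facility sizes, the plan's own ICC and a 35% rate in both arms. They concern declaring any difference, not meeting the 25% criterion. The fault lies in Protocol 9.2, the synopsis and the unresolved conflict, not in the SAP's use of a facility random effect.

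**What to change.** In Protocol 9.2 and the synopsis, replace the sentence on comparing proportions with:

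> The primary test is the study-arm coefficient of the random-effects logistic model in SAP 6.1 (facility and patient random effects), reported as an odds ratio with a two-sided 95% CI; arm proportions with cluster-adjusted CIs are descriptive only.

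Two further changes are needed so that a single primary analysis remains:
- Align the multilevel model in 9.2 (facility, patient ID and time as random effects) with the SAP model (facility and patient), or label it clearly as a separate exploratory model.
- Reconcile the primary population: ITT in 9.2 and the synopsis, per-protocol in SAP 6.1.

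The cost is a documented protocol amendment. Under Protocol 11.5 this needs approval and signature by the sponsor and Principal Investigator, and submission to the National Ethics Committee. No new data are needed, and the model is already planned in the SAP.
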